6.3.1.4. Recording of Adverse Events

Time Period for Collection of Adverse Events

Adverse events will be collected from first administration of the IMP throughout the treatment period up to and including the Follow-up Visit.

Serious adverse events will be recorded from the time of ICF.

Confirmed and suspected SARS-CoV-2 infection and COVID-19 will be recorded as adverse event.

Follow-up of Unresolved Adverse Events

Any AEs that are unresolved at the subject's last visit in the study are followed up by the Investigator for as long as medically indicated, but without further recording in ClinBaseTM.

AstraZeneca retains the right to request additional information for any subject with ongoing AE(s)/SAE(s) at the end of the study, if judged necessary.

Variables

The following variables will be collected for each AE:

- AE diagnosis/description
- The date and time when the AE started and stopped
- Intensity
- Whether the AE is serious or not
- Investigator causality rating against the investigational product (yes or no)
- AE caused subject's withdrawal from study (yes or no)
- Outcome

In addition, the following variables will be collected for SAEs:

- Date AE met criteria for serious AE
- Date Investigator became aware of serious AE
- AE is serious due to
- Date of hospitalisation
- Date of discharge
- Probable cause of death
- Date of death
- Autopsy performed

- Causality assessment in relation to study procedure(s)
- Causality assessment to other medication

The following intensity ratings will be used:

- 1 Mild (awareness of sign or symptom, but easily tolerated)
- 2 Moderate (discomfort sufficient to cause interference with normal activities)
- 3 Severe (incapacitating, with inability to perform normal activities)

It is important to distinguish between serious and severe AEs:

- Severity is a measure of intensity whereas seriousness is defined by the criteria in Section 6.3.1.2.
- An AE of severe intensity need not necessarily be considered serious. For example, nausea that persists for several hours may be considered severe nausea, but not a SAE. On the other hand, a stroke that results in only a limited degree of disability may be considered a mild stroke but would be an SAE.

Causality Collection

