10. EVALUATION AND CALCULATION OF VARIABLES

10.1. Safety Variables

10.1.1. Adverse Events

All AEs will be coded using the latest version of the MedDRA vocabulary, and will be listed for each subject.

Adverse events will be assigned to a treatment based on the start date/time of the AE in relation to dosing in that treatment period; for tabulation purposes the AE will then be assigned to the treatment received in the respective treatment period as follows:

- Treatment Period 1: AEs with start date/time at the time of or after dosing in Treatment Period 1 until the time of dosing in Treatment Period 2.
- Treatment Period 2: AEs with start date/time at the time of or after dosing in Treatment Period 2 until the time of dosing in Treatment Period 3.
- Treatment Period 3: AEs with start date/time at the time of or after dosing in Treatment Period 3 until the Follow-up Visit,

Adverse events with missing start dates/times will be handled as follows:

- Adverse events with unknown start times, but with start date known, will be imputed with a time of 00:00, unless the start date corresponds to any given dosing date. In this case the start time will be imputed with the time of dosing. If this results in a start date/time after end date/time of the AE, then the time will also be imputed with 00:00.
- Adverse events with completely unknown start dates will be imputed with the date and time of dosing, unless the end date is known and prior to dosing; in that case the start date will be imputed as the date of Screening and a time of 00:00.
- Adverse events with partially known start dates/times will be treated as follows:
 - If only the day is missing, then the day will be imputed with the first day of the month, unless the month and year in which the AE started is a month and year in which IMP was administered, then the day will be imputed with the first day on which IMP was administered in that month. If this results in a start date after the end date, then the day will be imputed with the first day of the month.
 - If only the month is missing and the year is a year in which IMP was administered, then the month will be imputed with the first month in which IMP was administered. If this results in a start date after the end date of the AE, then the month will be imputed with JAN. If the known year part is not a year in which IMP was administered, then the month will also be imputed with JAN.

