 - If both the day and month is missing and the year is a year in which IMP was administered, then the day and month will be imputed with the day and month of dosing. If this results in a start date after end date, then the day and month will be

imputed with 01JAN. If the year is not a year in which IMP was administered, then the day and month will also be imputed with 01JAN.

- If only the year is missing, then the year will be imputed with the year of dosing.

For purposes of the AE summaries, the following will apply:

- AEs with unknown intensity will be treated as "severe" for the tabulations.
- AEs with unknown relationship will be treated as "related" for the tabulations.
- AEs with unknown seriousness will be treated as "serious" for the tabulations.

There will be no imputation of AE data for the data listings. All data will be listed as recorded in the CRFs.

Adverse events with onset (start date/time) after dosing in Treatment Period 1, up to and including the final Follow-up visit will be summarised by treatment period and overall for all subjects, including tabulations by causality and severity (mild, moderate and severe). All tabulations will be presented by SOC and Preferred Term (PT). Furthermore, separate listings of SAEs, AEs that led to discontinuation (DAEs) and AEs that led to death will be presented.

Adverse events will be listed by subject and treatment, including the following information: verbatim term, SOC, PT and lowest level term, start date/time, end date/time, time from last dose, causality, action taken, whether the AE was classified as serious and the outcome.

All tabulations will include the number and percentage of subjects. In addition, a separate tabulation will be presented showing the number of events by treatment and PT.

Finally, an overview of all AEs will be presented, separately for the number and percentage of subjects and the number of events. This will include categories for any AE, AEs with outcome of death and SAEs

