11.2.5. Safety and Tolerability

All safety data (scheduled and unscheduled) will be presented in the data listings. Continuous variables will be summarised using descriptive statistics (n, mean, SD, minimum, median, maximum) by treatment. Categorical variables will be summarised in frequency tables (frequency and proportion) by treatment. The analysis of the safety variables will be based on the safety analysis set.

Adverse events will be summarised by PT and SOC using MedDRA vocabulary. Furthermore, listings of SAEs and adverse events that led to withdrawal will be made and the number of subjects who had any AE, SAEs, AEs that led to withdrawal, and AEs with severe intensity will be summarised. Adverse events that occur before dosing will be reported separately.

Tabulations and listings of data for vital signs, clinical laboratory tests and ECGs (listings only) will be presented. Any new or aggravated clinically relevant abnormal medical physical examination finding compared to the baseline assessment will be reported as an AE. Data will

be summarised for the observed values at each scheduled assessment, together with the corresponding changes from the baseline when baseline is defined. Clinical laboratory data will be reported in Système International units in the CSR.

Out-of-range values for safety laboratory will be flagged in individual listings as well as summarised descriptively using agreed standard reference ranges and/or extended reference ranges (eg, AZ, program, or laboratory ranges).

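### The rule for AEs with a missing month can date a post-dose AE before first dose or in an earlier treatment period, mostly at the expense of the cyclosporine and rifampicin columns

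*Combined protocol and SAP*

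**What the plan says.** Section 10.1.1 of the protocol sets the rule for a start date that lacks its month but falls in a dosing year: the recorded day is left as it is, and "then the month will be imputed with the first month in which IMP was administered". One check is attached to this: "If this results in a start date after the end date of the AE, then the month will be imputed with JAN".

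The same section allocates events to columns: "Adverse events will be assigned to a treatment based on the start date/time of the AE in relation to dosing in that treatment period". The first window opens at Period 1 dosing. The by-treatment summaries are limited to "Adverse events with onset (start date/time) after dosing in Treatment Period 1, up to and including the final Follow-up visit". Section 11.2.5 adds: "Adverse events that occur before dosing will be reported separately".

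Section 6.3.1.4 states the collection window: "Adverse events will be collected from first administration of the IMP throughout the treatment period". Only serious AEs are recorded earlier, from consent. Section 5.4.3 fixes the order: reference in Period 1, cyclosporine in Period 2, rifampicin in Period 3.

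**The concern.** The first dosing month is the earliest month a post-dose AE can belong to, so for such an AE the rule can only leave the date right or move it too early. The end-date check cannot catch this, because an earlier start never falls after the end. Its fallback, January, is earlier still.

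The neighbouring rules behave differently. With only the day missing in a dosing month, or with the whole date missing and no end date before dosing, the start goes to a dosing day. Unknown intensity, causality and seriousness are all set to the cautious value. The month-missing rule alone can produce a date outside the collection window and take an event out of every treatment column.

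Because the sequence is fixed, the later periods are the ones likely to fall in the second calendar month. The error therefore bears mainly on the combination columns, which the safety objective is about.

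**Working it through.** The plan gives no figure to reproduce, so the check applies the rule to every possible onset day.

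**Inputs**
- Period 1 to Period 2 dosing: 4 or 5 days (assumption; Section 3.1 has no washout here, and the 96-hour sample is on Day 5).
- Period 2 to Period 3 dosing: 14 days, the minimum in Section 3.1.
- Follow-up: 7 or 14 days after the last dose, the limits in Section 3.1.
- First-dose dates: each of the 62 days from 1 July to 31 August 2020 (assumption, based on the synopsis dates of July for first enrolment and September for last completion).
- Onset: equally likely on every day of a column, or only on Days 1-5 of each period (assumptions).

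**Formula.** Let k be the days from first dose to true onset. If onset falls in the next month and k is below 31, its day of the month is lower than that of first dose, so the imputed date is before first dose. July and August each have 31 days, so k of every 31 first-dose dates lead to this. The share at day k is k/31 for k up to 30, and a column's share is its mean k divided by 31.

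| Column and onset pattern | 4-day gap | 5-day gap |
|---|---|---|
| Reference | k 0-3: 1.5/31 = 4.8% | k 0-4: 2/31 = 6.5% |
| Cyclosporine, all days | k 4-17: 10.5/31 = 33.9% | k 5-18: 11.5/31 = 37.1% |
| Cyclosporine, Days 1-5 | k 4-8: 6/31 = 19.4% | k 5-9: 7/31 = 22.6% |
| Rifampicin, all days, Follow-up at 7 days | k 18-25: 21.5/31 = 69.4% | k 19-26: 22.5/31 = 72.6% |
| Rifampicin, Days 1-5 | k 18-22: 20/31 = 64.5% | k 19-23: 21/31 = 67.7% |

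With Follow-up at 14 days, rifampicin onsets run to k = 32 or 33. From k = 31 the imputed date normally reaches the first-dose day or later, so the AE lands in the reference column. Direct enumeration gives 67.5% (4-day gap) or 64.2% (5-day gap) before first dose, and a further 13% or 19% moved to reference.

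Limiting first-dose dates so that follow-up ends by 30 September widens the ranges to 3-7%, 17-37% and 60-73%. In all these 14-day cases, 93-99% of the AEs wrongly dated before dosing belong to Periods 2 and 3.

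**Example.** First dose 20 July, cyclosporine 24 July, rifampicin 7 August. An AE starting 8 August with the month missing becomes 8 July, 12 days before first dose, and enters no treatment column. An AE starting 21 August becomes 21 July and is counted under reference.

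**Longer interval.** Section 3.1 allows the three periods up to 36 days. Counting Day -1 of Period 1 as day 1 and Day 5 of Period 3 as day 36, first dose is day 2 and Period 3 dosing is day 32. That is 30 days apart, or 26 days after Period 2 with a 4-day gap. Rifampicin Days 1-5 are then k = 30 to 34. Apart from a few onsets in a third calendar month, only k = 30 goes before first dose: (30/31)/5 = 19%. The other four of five days land 0 to 3 days after first dose, in the reference column.

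**Absolute size.** One misplaced AE changes a column by at most one subject in 14, or 1/14 = 7.1 percentage points.

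**The case against.** The strongest reply is that the rule will hardly ever be used. It needs a known day and year with an unknown month. Section 6.3.1.4 collects start date and time and asks about health since the last questioning. Subjects are resident for Periods 1 and 2 up to Day 5 and again for Period 3 up to Day 5. Capture is electronic at source, and queries repeat until discrepancies are resolved (Sections 9.4 and 9.5). With 14 subjects, such records should be close to none. This stands, and it limits the importance of the point.

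A reader might infer that the affected events vanish from the report. The documents do not support that. Section 10.1.1 leaves the listings un-imputed, AEs before dosing are reported separately, and a data review meeting precedes hard lock (Section 11.3). The events leave the treatment tables only.

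A reader might also infer that every second-month AE becomes pre-dose. That is not so either: some move to an earlier treatment column, and with a long interval most rifampicin AEs do.

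Finally, a pre-dose date can be correct for a serious AE recorded during screening. A plain floor at first dose would turn such an event into a treatment-emergent one, possibly starting after it ended. This stands, and the fix has to allow for it.

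None of these points makes the rule right when it is used. Section 11.2.1 says that no separate SAP will be written, so this text is what will be programmed.

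**Conclusion.** The point holds as a defect in a stated rule, with a small practical effect. The rule can date a post-dose AE before first dose, which contradicts the collection window for non-serious AEs, or in an earlier treatment period. With a 14-day interval the shares dated before first dose are about 5-7% for reference, 19-37% for cyclosporine and 64-73% for rifampicin.

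These are shares of possible onset days among AEs whose month is missing. They are not expected event counts. They rest on the assumed 4- or 5-day gap, the July-August first-dose dates and the onset pattern. What does not depend on those choices is the direction: for a post-dose AE, any error moves the event earlier and mainly out of the combination columns. The documents give no ground for going further and saying that the study's safety conclusions would be materially biased.

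**What to change.** Replace the month-missing imputation in Section 10.1.1, for records whose year is a dosing year, with:

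> Where the day and year are known but the month is not, consider the months that give a date from first IMP dose to the Follow-up Visit and not after the AE end date. If there is one, use it. If there is more than one, use the month that assigns the AE to the most recent treatment. If there is none and the AE ended before first dose (for example an SAE recorded during screening), keep it as pre-dose, using the latest month that gives a date on or after informed consent and not after the end date. If there is none otherwise, impute the date and time of first dose.

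This also corrects AEs that the present rule moves to an earlier treatment column. Simply resetting early dates to first dose would not work, because it would move combination-period AEs into the reference column.

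The cost is one paragraph and a few lines of code, with no change to data collection. The small downside is that an ambiguous AE may be charged to a combination treatment. With a 14-day interval and Follow-up at 7 days this cannot happen, since the span of 25 or 26 days (4 or 5 + 14 + 7) is shorter than a month. With Follow-up at 14 days the span is 32 or 33 days, so an AE from the first two or three days of Period 1 can have a second candidate date under rifampicin unless its end date rules that out. Longer intervals leave more such days.

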10.1.2. Laboratory Assessments

Haematology and clinical chemistry values will be listed by subject and time point including changes from baseline and repeat/unscheduled measurements. Summary tabulations including absolute value and changes from baseline will be presented by treatment period and time point for the safety analysis set. The baseline for the measurements will be the last assessment performed prior to dosing in Treatment Period 1. Changes from baseline will be calculated and presented for all post-baseline time points including the Follow-up Visit. Shift tables will also be presented.

Any laboratory parameters with results from the laboratory given as "< xx" or ">xx" in the database will be imputed with the absolute value of the number without the sign (eg, < 2.2 will be imputed as 2.2) for the descriptive statistics and changes from baseline.

The listings will include the following information: test name, date of measurement, reference range, result and flags for any measurements that are outside the reference range (eg, AstraZeneca, program, or laboratory ranges). Clinical laboratory data will be reported in System International units in the CSR.

Additional listings will be presented for the following:

- Urinalysis (macroscopic and microscopic, if applicable)
- The results of viral serology and the drugs of abuse and alcohol screen will not be listed in the CSR

10.1.3. Physical Examination and Body Weight

The baseline/screening results of the physical examination will be documented in medical history for each subject.

Any new or aggravated clinically relevant abnormal medical physical examination finding compared to the baseline assessment will be reported as an AE.

10.1.4. Resting 12-lead Electrocardiogram

For each subject, 12-Lead ECG results will be listed, including classifications as "Normal", "Abnormal, clinically significant" and "Abnormal not clinically significant".

10.1.5. Vital Signs

The results of the vital signs measurements will be listed by subject and time point including the date/time of the assessment, changes from baseline and repeat/unscheduled measurements. The baseline for vital signs measurements will be last assessment prior to dosing in Treatment Period 1. Descriptive statistics will be presented by treatment and time point for both observed values and changes from baseline.

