3. STUDY DESIGN

3.1. Overall Study Design and Flow Chart

This study will be an open-label, 3-period, 3-treatment, fixed-sequence study in healthy subjects (males and females of non-childbearing potential), performed at a single Clinical Unit.

The study will comprise of the following periods (visits):

- A Screening Period of maximum 28 days (Visit 1);
- A fixed sequence of 3 Treatment Periods during which subjects will be resident at the Clinical Unit from one day prior to administration of verinurad+allopurinol (Day -1) of Treatment Period 1 until the morning of Day 5 of the Treatment Period 2, and similarly between Day -1 to Day 5 of Treatment Period 3. There will be a washout period of 14

days between Treatment Periods 2 and 3 dosing. The 3 Treatment Periods, including the washout period, will be a total of up to 36 days (Visits 2 to3);

• A Follow-up Visit within 7 to 14 days after the last administration of verinurad+allopurinol (Visit 4).

Subjects will be resident at the Clinical Unit from Day -1 of Treatment Period 1 (Visit 2), ie, prior to the evening meal the night before first dosing with verinurad+allopurinol, until the morning of Day 5 of Treatment Period 2, ie, at least 96 hours after the second dosing with verinurad+allopurinol. There will be no washout between Treatment Period 1 and Treatment Period 2. Subjects will be resident continuously for the full duration of Treatment Periods 1 and 2. There will be a minimum washout period of 14 days between dosing in Treatment Period 2 and dosing in Treatment Period 3. Subjects will not be required to be resident at the Clinical Unit for around 10 days during the washout period. Subjects will be resident again from Day -1 of Treatment Period 3 (Visit 3), ie, prior to the evening meal the night before third (last) dosing with verinurad+allopurinol, until the morning of Day 5 of Treatment Period 3, ie, at least 96 hours after the last dosing with verinurad+allopurinol. The subjects will return for a Follow-up Visit in 7-14 days after the last verinurad+allopurinol dose.

Each subject will receive a single dose of verinurad+allopurinol on 3 occasions, under fasted conditions. Each subject will also receive a single dose of cyclosporine on 1 occasion and a single dose of rifampicin on 1 occasion, with cyclosporine and rifampicin being dosed on separate occasions and always together with verinurad+allopurinol.

Details on IMP administration is provided in Section 5.4.3.

Figure 3-1 Study Flow Chart

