Blood sampling for analysis of verinurad, M1, M8, allopurinol and oxypurinol plasma concentrations			Xi	Xi		Xi		Section 6.4.2
Exploratory blood sampling for analysis of cyclosporine blood concentrations				Xi				Section 6.4.2
Exploratory blood sampling for analysis of rifampicin plasma concentrations						Xi		Section 6.4.2

Abbreviations: AE = Adverse event; BMI = Body mass index; ECG = Electrocardiogram; FSH = Follicle stimulating hormone; HBc = Hepatitis B core; HIV = Human immunodeficiency virus; HLA-B = Human leukocyte antigen B; SAE = Serious adverse events;

Study Assessments	Visit 1		Visit	2	Vis	it 3	Visit 4	Corresponding Section in
	Screening	Treat Peri		Treatment Period 2	Treat Peri		Follow-up or Early Termination	Protocol
	Day -28 to -2	Day -1	Days 1 to 5	Days 1 to 5	Day -1	Days 1 to 5	7-14 days after last verinurad dose	

- ^a Subjects will be allowed to leave (discharged from) the clinical unit after the last PK sample is taken at 96 hours after dosing (Day 5).
- b Occurs on Day 1, in each Treatment period (considered as the 0 hour time point)
- Subjects will be contacted within 24 hours before a scheduled visit to the Clinical Unit to confirm that no signs and/or symptoms of COVID-19 are present and that no subject had any contact with a known SARS-CoV-2 positive tested person within the last 14 days. In the case that a subject confirms signs and/or symptoms or has had contact with a SARS-CoV-2 positive person, the visit will be canceled and the reason for the cancellation will be appropriately documented.
- d Only SAEs will be recorded during the Screening period and on Day -1 Treatment Period 1 (Visit 1)
- ^e Blood pressure, pulse rate (supine) and temperature (tympanic) will be taken at pre-dose and 1.5, 4, and 6 hours after dosing on Day 1 and on Days 2, 3, 4 and 5 in each Treatment Period.
- In Treatment Period 1, urine samples and blood for clinical chemistry will be collected on Days 1, 2 and 3. Urine samples will include only the measurement of sodium, creatinine, lactic acid, potassium, aldosterone and pH. Blood samples will include only the measurement of creatinine, cystatin-C and sodium.
- Blood for haematology will be collected on Day 3 only.
- ^h A full physical exam will occur at the Screening and Follow-up Visits. A brief physical exam will occur on Day -1 and Day 3 in each Treatment Period.

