3.3.3. Cyclosporine

Cyclosporine is a commercially available systemic immunosuppressant with a known safety and efficacy profile.

Although the mode of action is not fully understood, studies suggest that cyclosporine inhibits the development of cell-mediated reactions, including allograft immunity, delayed cutaneous hypersensitivity, experimental allergic encephalomyelitis, Freund's adjuvant arthritis, graft-versus-host disease, and also T-cell dependent antibody production. At the cellular level it inhibits production and release of lymphokines including interleukin 2 (T-cell growth factor, TCGF). Cyclosporine appears to block the resting lymphocytes in the G0 or G1 phase of the cell cycle and inhibits the antigen-triggered release of lymphokines by activated T-cells. All available evidence suggests that cyclosporine acts specifically and reversibly on lymphocytes. Unlike cytostatic agents, it does not depress haemopoiesis and has no effect on the function of phagocytic cells.

Cyclosporine has a half-life of 6 hours in healthy volunteers, and discharge from the Clinical Unit at 96 hours post-dose deemed appropriate.

Some cyclosporine side effects are related to the cardiovascular system (hypertension) and central nervous system (tremor, headache, convulsions, paraesthesia, encephalopathy) and would theoretically influence the subject who has COVID-19 but these effects would pose minimal risks in healthy volunteers and short duration of treatment (such as a single dose of 600 mg cyclosporine).

Cyclosporine has been reported to inhibit the replication of diverse coronaviruses in vitro but this effect is not confirmed for SARS-CoV-2. In addition, cyclosporine may be beneficial in severe stages of COVID-19 based on inhibition on pro-inflammatory IL-2.

On consideration of the benefit/risk due to the COVID-19 pandemic, the single dose of cyclosporine is not considered to add any additional risk to the subjects, such as a reduction of the efficacy of the immune system.

Please refer to the Summary of Product Characteristics of cyclosporine capsules for details on PK, PD and safety [17].

Reports suggest that the plasma concentration of cyclosporine may be increased during concomitant treatment with allopurinol. The possibility of enhanced cyclosporine toxicity should be considered if the drugs are co-administered [1].

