11.2. Methods of Statistical Analyses

11.2.1. General Principles

The statistical methodology below describes the statistical analysis as it is foreseen when the study is being planned.

If circumstances should arise during the study rendering the analysis inappropriate, or if in the meantime improved methods of analysis should come to light, different analyses may be performed. A separate SAP will not be written for the study. Any deviations from the statistical methodology defined in this protocol, reasons for such deviations and all alternative/additional statistical analyses that may be performed will be described in the CSR. Such changes to analyses may be written into an abbreviated SAP, if appropriate. The verification and review of all statistical modeling assumptions will be documented appropriately.

All original and derived parameters as well as demographic and disposition data will be listed and described using summary statistics. All safety data (scheduled and unscheduled) will be presented in the data listings.

Demographic and baseline data will be summarised overall for all dosed subjects. Pharmacokinetic data will be summarised by treatment. Safety and tolerability data will be summarised by treatment period, if applicable.

Frequency counts (number of subjects [n] and percentages) will be made for each qualitative variable. Descriptive statistics for safety data (n, mean, SD, median, minimum and maximum) will be calculated for each quantitative variable (unless otherwise stated). Descriptive statistics will only be presented if n > 3. If no subjects have data at a given time point, then only n=0 will be presented. If n < 3, only the n, minimum, and maximum will be presented. If n=3, only the n, minimum and maximum will be presented; the other descriptive statistics will be left blank.

The following rules will apply to any repeated safety assessments occurring within each treatment period:

- If the repeated measurement of a specific parameter occurs prior to IMP administration (Day 1), then the last obtained value prior to dosing will be used in the descriptive statistics and in the calculation of changes from baseline;
- If the repeated measurement of a specific parameter occurs after IMP administration (Day 1), then the first (non-missing) value after dosing will be used in descriptive statistics and in the calculation of changes from baseline.

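### Vital-sign changes in the cyclosporine and rifampicin periods are summarised only from the pre-Period 1 baseline, so between-period drift enters them in full; a within-period change should be added

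*Combined protocol and SAP*

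**What the plan says.** Section 10.1.5 sets the baseline for vital signs: "The baseline for vital signs measurements will be last assessment prior to dosing in Treatment Period 1". It continues: "Descriptive statistics will be presented by treatment and time point for both observed values and changes from baseline". Section 11.2.5 also summarises observed values and changes, and defines no other baseline.

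Footnote e to Table 3-1 (Section 3.1) schedules blood pressure, pulse rate and temperature at "pre-dose and 1.5, 4, and 6 hours after dosing on Day 1 and on Days 2, 3, 4 and 5 in each Treatment Period". A pre-dose reading therefore exists in each of the three periods.

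On the design, Section 3.1 states: "This study will be an open-label, 3-period, 3-treatment, fixed-sequence study in healthy subjects". Period 1 is verinurad+allopurinol alone, Period 2 adds cyclosporine and Period 3 adds rifampicin. Between the first two, "There will be no washout between Treatment Period 1 and Treatment Period 2", and subjects stay in the unit. At least 14 days separate the Period 2 and Period 3 doses, around 10 of them spent outside the unit.

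Section 10.1.2 uses the same single pre-Period 1 baseline for laboratory values. Under Table 3-1, haematology is sampled on Day -1 of Periods 1 and 3 and on Day 3 of every period. Period 2 has no Day -1.

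**The concern.** A by-treatment table of change from baseline will be read as change under that treatment. Here the Period 2 and Period 3 columns also contain whatever happened to the subject between the Period 1 baseline and the later dose: habituation to the unit, days of residence and, for Period 3, going home and coming back. Every subject takes the treatments in the same order, so this drift does not average out across treatments.

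Safety and tolerability of the combinations is a secondary objective, and vital signs are a named outcome in Table 2-2. Section 3.3.3 lists hypertension among the side effects of cyclosporine. Table 3-1 schedules ECGs only at Screening and Follow-up, so blood pressure and pulse are the scheduled quantitative cardiovascular readings in the days after each inhibitor is given. A change summary that mixes drift with response is less useful than it could be, when the data for a cleaner one are already collected.

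**Working it through.** **Timing (Section 3.1).** Period 1 runs 96 h from dose to last sample and Period 2 follows without washout, so Period 2 dosing is about 4 days after the baseline. Period 3 dosing is at least 4 + 14 = 18 days after it.

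**Identity.** Let pre_k and post_k be a subject's pre-dose and post-dose values in period k. The planned change is

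post_k - pre_1 = (post_k - pre_k) + (pre_k - pre_1).

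The first term is the within-period change and the second is drift up to the dose. Drift has coefficient 1. In Period 1 it is zero, so only Periods 2 and 3 are affected.

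**Numerical check.** The documents give no drift size, so these are assumptions: 14 subjects, between-subject SD 10, within-subject SD 5, no true treatment effect.

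| Assumed drift | Mean change from Period 1 baseline | Mean change from own period's pre-dose value |
|---|---|---|
| 0 | -0.01 | 0.01 |
| -2 | -2.0 | 0.0 |
| -5 | -5.01 | 0.0 |
| +3 | 3.01 | 0.02 |

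Departures from the exact values are simulation error.

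**What the other planned tables show.** Suppose the mean is M before Period 1, drift is -5, and the true rise after dosing is +5. The observed means are then M (Period 1 pre-dose), M - 5 (later pre-dose) and M (later post-dose). The change table reports M - M = 0. The observed-value table gives M - (M - 5) = +5, provided the same subjects contribute to both means. The mean is therefore recoverable. The SD, median, minimum and maximum of post_k - pre_k are not, because they depend on within-subject pairing that summary tables do not carry; they would have to be rebuilt from the listings.

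**Is the period's own pre-dose value usable?** Section 1.1.1.1 gives a verinurad half-life of 13 h, so the Period 2 pre-dose value falls 96/13 = about 7 half-lives after the Period 1 dose. Section 3.3.3 gives 6 h for cyclosporine, and 14 × 24/6 = 56 half-lives pass before Period 3. No oxypurinol half-life is given, so some residual effect before Period 2 cannot be excluded. That is a reason to show both changes.

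**Haematology.** The last scheduled sample before Period 2 dosing is Period 1 Day 3, taken after verinurad+allopurinol, so it is not a pre-treatment baseline. For Period 3, the Day -1 sample is available.

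**The case against.** The strongest defence is that the Period 1 baseline is the only one that precedes all study drug. With no washout before Period 2, that period's pre-dose value follows active treatment. Change from the untreated state is a legitimate safety display, and this stands: it argues for adding a column, not for replacing one. It is also true that observed values are tabulated, that individual values are listed, and that nothing inferential or primary depends on these tables. A period-specific baseline does not remove time-of-day or other within-period effects either.

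Three stronger readings are tempting, and the documents do not support them.

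- A reader might infer that the change tables are the only quantitative view of blood pressure under each inhibitor. They are not: Sections 10.1.5 and 11.2.5 also summarise observed values, including each period's pre-dose reading.
- A reader might see a conflict with Section 11.2.1, which says that for a repeated pre-dose measurement "then the last obtained value prior to dosing will be used in the descriptive statistics and in the calculation of changes from baseline". That rule chooses among repeats within a period. Its companion rule for post-dose repeats uses the same phrase about changes from baseline, so the phrase covers values entering the calculation and does not define a baseline.
- A reader might claim a sizeable gain in precision for cyclosporine. With equal variances, the ratio of the SDs of change is √((1 - ρ_same)/(1 - ρ_across)). Assumed correlations of 0.7 to 0.8 within a day and 0.5 across at least 18 days give √(0.3/0.5) = 0.77 and √(0.2/0.5) = 0.63, a reduction of 23% to 37%. That concerns only same-day readings in Period 3. For Period 2, an assumed 0.7 across 4 days gives √(0.3/0.3) = 1 to √(0.2/0.3) = 0.82, a reduction of 0% to 18%. None of these correlations comes from the documents.

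Nor should the clinical stakes be inflated. Section 3.3.3 names hypertension as one of several cyclosporine effects and regards them as posing minimal risk in healthy volunteers given a single dose.

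**Conclusion.** The point holds as a minor improvement. That drift enters the Period 2 and Period 3 change tables one-for-one follows from the baseline definition and the fixed sequence, and needs no assumption. Its size in mmHg or beats per minute is unknown; the figures of -5 to +3 are illustrations. Mean drift can be seen in the planned output. The gap is that the distribution of within-period change is not summarised for any treatment other than the reference. The documents do not support calling the Period 1 baseline an error, or replacing it.

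**What to change.** In Section 10.1.5, add change from the last pre-dose value of the same Treatment Period, summarised by treatment and time point. Keep change from the Period 1 baseline alongside it, labelled as change from the untreated state. In Section 10.1.2, add for haematology in Period 3 only the change from Day -1 of that period. Leave the Period 2 haematology baseline and Section 11.2.1 as they are.

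The cost is two sentences and one extra column in the affected tables. No assessment, visit or blood sample is added. Section 11.2.1 says no separate SAP is planned, so the protocol, or the abbreviated SAP that it allows, is the place to record this.
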